## 1 Introduction

---

The utilization of soft toric contact lenses has increased significantly over the past few years. Toric contact lens wearers demand two things from their contact lenses, great comfort and excellent vision. CooperVision's Avaira Vitality™ toric uses a third generation silicone hydrogel material which makes the lens inherently wettable with no surface treatments, and uses naturally wettable building blocks to improve compatibility between silicone and hydrophilic domains. This, combined with the higher water content of Avaira Vitality™ toric ensures a high performing, comfortable lens.

ACUVUE OASYS® for Astigmatism contact lenses with HYDRACLEAR® PLUS technology helps to stabilize the tear film, minimizing dryness and maintaining moisture for exceptional comfort and vision stability. Therefore, CooperVision is interested in evaluating the clinical performance of the Avaira Vitality™ toric and ACUVUE OASYS® for Astigmatism lenses when existing wearers of hydrogel toric lenses are refitted with these lenses over 2-weeks of daily wear.

## 2 Study Objective

---

The aim of this prospective study is to evaluate the clinical performance of existing soft contact lens wearers with astigmatism when refitted with Avaira Vitality™ toric and ACUVUE OASYS® for Astigmatism lenses over 2-weeks of wear.

**The primary variables of interest are:**

- Lens fitting characteristics

**The secondary variables of interest are:**

- Wearing times (average and comfortable)

\* Lens fit preference judged by the study investigator

## 3 Study Hypothesis

---

### 3.1 Study Hypothesis

---

- Null hypothesis (Ho): There is no difference in lens fitting characteristics between the two hydrogel toric lenses for the key variables tested.
- Alternative hypothesis (H1): There is a difference in lens fitting characteristics between the two hydrogel toric lenses for the key variables tested.

## 4 Study Design

---

This is a 40-subject, prospective, randomized, double masked; bilateral, 2 week cross-over study comparing the fitting characteristics of senofilcon A toric lenses against fanfilcon A silicone hydrogel toric lenses (table 1). [REDACTED]

[REDACTED]

[REDACTED]

[REDACTED]

[REDACTED]

[REDACTED]

[REDACTED]

## 5 Investigational Sites

---

### 5.1 Number of Sites

---

This will be a single center investigational site in Mexico City. (Target 40 subjects).

### 5.2 Investigator Recruitment

---

This study will be conducted at the School of Optometry Clinic; National Autonomous University (UNAM) Mexico City. The Investigators will be required to fulfil the following criteria:

- Licensed Optometrist with at least two years of contact lens fitting experience.
- Experienced Investigators who will be trained in Good Clinical Practice (GCP) by the principal investigator.
- In-office email or fax.
- Willingness to follow the study protocol and to co-operate with the study monitors.

This clinical study is designed to be in conformance with the ethical principles in the Declaration of Helsinki, with the ICH guidelines for Good Clinical Practice (GCP) and all the applicable local guidelines.

## **6 Ethics Review / Statement of Compliance**

---

### **6.1 Relevant Standards / Guidelines**

---

This implementation document has been developed in accordance with the following:

- ICH Harmonized Tripartite Guideline for Good Clinical Practice
- Declaration of Helsinki

### **6.2 Institutional Review Board**

---

This study will be conducted in accordance with Institutional Review Board regulations (U.S. 21CFR Part 56.103) or applicable IEC regulations. Copies of all IRB/IEC correspondence with the investigator/sponsor will be kept on file. The study will commence upon approval from the following Ethics Committee: Comisión de Ética de la FESI. [name]. [contact] and email address [contact].

### **6.3 Clinical Trial Registration**

---

This study will be registered with clinicaltrials.gov in accordance with section 801 of the Food and Drug Administration (FDA) Act which mandates the registration of certain clinical trials of drugs and medical devices.

### **6.4 Informed Consent**

---

Informed consent shall be obtained in writing from the subject and the process shall be documented before any procedure specific to the clinical investigation is carried out.

## **7 Potential Risks and Benefits to Human Subjects**

---

There may be direct benefits to the subjects in this study such as improved vision, comfort, convenience, and cosmetic advantage. Participation in a study may contribute to scientific research information that may be used in the development of new contact lens products. In addition, subjects will receive an examination of the front part of their eyes and may have the opportunity to try a different type of soft contact lenses and/or different lens care products at no cost to them. The contact lens materials used in this study are commercially available as daily or extended wear. This study will investigate participants' wearing schedule intended for daily

wear (NOT extended wear) similar to the average wearing time of 10-16 hours for daily wear lenses.

This study is considered to be a non-significant risk study based on United State Food and Drug administration (FDA) and International Standards Organization (ISO) guidelines because the study devices used as intended in this study (daily wear) don't represent a potential for serious risk to the health, safety or welfare of the subject, and (2) it is not an implant, (3) it is not used to support or sustain human life, (4) it is not of substantial importance in diagnosing, curing, mitigating or treating disease or otherwise prevents impairment of human health, (5) does not present a potential for serious risk to the health, safety or welfare of the subject (Appendix 2).

Complications that may occur during the wearing of contact lenses include discomfort, dryness, aching or itching eyes, excessive tearing, discharge, hyperemia and variable or blurred vision. More serious risks may include photophobia, iritis, corneal edema or eye infection. Although contact lens-related infections are very infrequent, the possibility does exist. The incidence of infection due to day-wear soft lenses is 0.035%. Almost always an infection will occur only in one eye. This risk is assumed by 35-million Americans who currently wear contact lenses.

Routine clinical procedures including auto-refraction, auto-keratometry, visual acuity, anterior ocular health assessment, and contact lens fitting will be used. In addition, high magnification imaging of the lens fit may be made using 35 mm or digital cameras, in vivo confocal microscopy, and/or specular microscopy. Patients will be monitored every two weeks until the end of the study to reduce if not eliminate the occurrence of adverse or potential adverse events. Patients will be given instructions from their ECP regarding early symptoms and signs of adverse events and their contact information.

## 8 Materials and Methods

---

### 8.1 Participants

---

Approximately **40 habitual** soft contact lens wearers will be enrolled. Each subject will be required to attend up to **four** scheduled study visits over a period of approximately two months.

Each subject will be given a unique ID number. Additionally, all subjects must meet the study inclusion and exclusion criteria listed below.

#### Inclusion criteria

A person is eligible for inclusion in the study if he/she:

- Is between 18 and 40 years of age (inclusive)
- Has had a self-reported visual exam in the last two years
- Is an adapted soft contact lens wearer
- Has a contact lens spherical prescription between +6.00 to - 9.00 (inclusive)
- Have no less than -0.75D of astigmatism and no more than -2.25 D in both eyes.

- Can achieve best corrected spectacle distance visual acuity of 20/25 (0.10 logMAR) or better in each eye.
- Can achieve a distance visual acuity of 20/30 (0.18 logMAR) or better in each eye with the study contact lenses.
- Has clear corneas and no active ocular disease
- Has read, understood and signed the information consent letter.
- Patient contact lens refraction should fit within the available parameters of the study lenses.
- Is willing to comply with the wear schedule (at least 5 days per week, > 8 hours/day assuming there are no contraindications for doing so).
- Is willing to comply with the visit schedule

## **Exclusion Criteria**

A person will be excluded from the study if he/she:

- Has a CL prescription outside the range of the available parameters of the study lenses.
- Has a spectacle cylinder less than -0.75D or more than -2.50 D of cylinder in either eye.
- Has a history of not achieving comfortable CL wear (5 days per week; > 8 hours/day)
- Has contact lens best corrected distance vision worse than 20/25 (0.10 logMAR) in either eye.
- Presence of clinically significant (grade 2-4) anterior segment abnormalities
- Presence of ocular or systemic disease or need of medications which might interfere with contact lens wear.
- Slit lamp findings that would contraindicate contact lens wear such as:
  - Pathological dry eye or associated findings
  - Pterygium, pinguecula, or corneal scars within the visual axis
  - Neovascularization > 0.75 mm in from of the limbus
  - Giant papillary conjunctivitis (GCP) worse than grade 1
  - Anterior uveitis or iritis (past or present)
  - Seborrheic eczema, Seborrheic conjunctivitis
  - History of corneal ulcers or fungal infections
  - Poor personal hygiene
- Has a known history of corneal hypoesthesia (reduced corneal sensitivity)
- Has aphakia, keratoconus or a highly irregular cornea.
- Has Presbyopia or has dependence on spectacles for near work over the contact lenses.
- Has undergone corneal refractive surgery.
- Is participating in any other type of eye related clinical or research study.

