#### Visit 1a: Baseline habitual lenses

The following baseline measurements and assessments will be recorded:

[REDACTED]

[REDACTED]

- Habitual lens wearing times:

[REDACTED]

- Average daily wearing time (hours/day)
- Average comfortable wearing time (hours/day)

[REDACTED]

[REDACTED]

[REDACTED]

[REDACTED]

[REDACTED]

[REDACTED]

[Redacted text block]

[Redacted text block]

- [Redacted]
- [Redacted]
- [Redacted]
- [Redacted]
- [Redacted]

[Redacted text block]

[Redacted text block]

• Lens Fit

- Lens centration (centered/slightly decentered/substantially decentered)
- Corneal coverage [Y/N]
- Post-blink movement (0-5 Likert scale)

[Redacted text block]

[Redacted text block]

[Redacted text block]

[Redacted text block]

[Redacted text block]

[Redacted text block]

[Redacted text block]

[Redacted text block]

[Redacted text block]

[REDACTED]  
[REDACTED]  
[REDACTED]  
[REDACTED]

- Complete the eligibility checklist.
- If at this point the subject is found to be ineligible, then complete an Exit form and exit the subject from the study.

Visit 1 b: Fitting visit

If eligible, complete the Enrolment Log and identify the test lens from Appendix 4. The subjects will undergo a trial fit in both eyes with both study lenses (e.g. Avaira Vitality™ toric and ACUVUE OASYS® for ASTIGMATISM, according to manufacturer’s fitting guides) [REDACTED]

[REDACTED] If the lenses are not suitable to be dispensed then the subject will be discontinued and an Exit form will be completed.

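### Does the 20/25 contact-lens acuity exclusion contradict the 20/30 limit with the study lenses?

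*Combined protocol and SAP*

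**What the plan says.** Three acuity lines appear in section 8.1 of the protocol.

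- Inclusion, spectacles: "Can achieve best corrected spectacle distance visual acuity of 20/25 (0.10 logMAR) or better in each eye".
- Inclusion, study lenses: "Can achieve a distance visual acuity of 20/30 (0.18 logMAR) or better in each eye with the study contact lenses".
- Exclusion, contact lenses: "Has contact lens best corrected distance vision worse than 20/25 (0.10 logMAR) in either eye".

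The two inclusion lines name the correction under which acuity is measured. The exclusion line says contact lenses and best corrected, but not which lenses. The opening of section 8.1 states that "all subjects must meet the study inclusion and exclusion criteria listed below".

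In section 8.3.1 the eligibility checklist closes Visit 1a, which covers the habitual lenses. Visit 1b then begins: "If eligible, complete the Enrolment Log and identify the test lens from Appendix 4". Next comes the fitting itself: "The subjects will undergo a trial fit in both eyes with both study lenses". A subject for whom the trial lenses prove unsuitable is withdrawn at that point.

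The cylinder limits also differ. Inclusion reads "Have no less than -0.75D of astigmatism and no more than -2.25 D in both eyes", with no plane stated. Exclusion reads "Has a spectacle cylinder less than -0.75D or more than -2.50 D of cylinder in either eye".

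**The concern.** Read quickly, the lists set two limits for one quantity. A subject who sees 20/30 through a study lens meets the inclusion line and, if the exclusion line also refers to study lenses, triggers it. The 20/30 limit would then never decide a case, and an investigator working from one line could enrol a subject whom a colleague working from the other would exit. At stake would be consistent screening and an accurate description of who was enrolled.

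The cylinder limits raise a smaller version of the same doubt. On a single scale, an eye at -2.50 D is not admitted by one list and not excluded by the other.

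**Working it through.** **Inputs.** Limits of 20/25 (0.10 logMAR) and 20/30 (0.18 logMAR), and cylinder limits of -2.25 D and -2.50 D, all from section 8.1. Cylinder powers of both lenses stop at -2.25 D (section 8.2.1, Table 1). Assumptions from outside the documents: 0.02 logMAR per letter and a 12 mm vertex distance.

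**Step 1: reproduce the printed conversions.** logMAR = log10(denominator / 20).
- log10(25/20) = 0.097, printed as 0.10.
- log10(30/20) = 0.176, printed as 0.18.
- Difference: 0.176 - 0.097 = 0.079 logMAR; 0.079 / 0.02 = about 4 letters.

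**Step 2: apply both lists on the reading that causes trouble.** Eligible means inclusion met and exclusion not triggered. Both lines are taken as study-lens acuity.

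| Study-lens logMAR | 20/30 inclusion | 20/25 exclusion | Outcome |
|---|---|---|---|
| 0.00 | met | not triggered | in |
| 0.10 | met | not triggered | in |
| 0.18 | met | triggered | out |
| 0.30 | not met | triggered | out |

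Every row has one outcome. Meeting an inclusion line while triggering an exclusion is how paired lists ordinarily work, and the subject is out. The cost of this reading is a redundant line.

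**Step 3: the other readings.**
- *Habitual lenses.* The 20/25 line is tested on the lenses worn to Visit 1a and the 20/30 line on the study lenses. They are different measurements and both limits operate.
- *Contact lenses with over-refraction.* The 20/25 line tests what the eye can reach, and the 20/30 line tests what the study lens delivers. Both limits operate.

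The change of wording between the two lines favours one of these readings. So does the visit order: the checklist follows the habitual-lens assessments, and the suitability decision after the Visit 1b fitting gives the study-lens line a place to operate.

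**Step 4: cylinder.** On one scale, -2.50 D fails inclusion and so stays out; the -2.25 D limit decides. If the exclusion is in the spectacle plane and the inclusion at the cornea, convert each meridian with F / (1 - 0.012F). For a -4.00 D sphere with a -2.50 D cylinder:
- -6.50 / 1.078 = -6.03 and -4.00 / 1.048 = -3.82, so the corneal cylinder is about -2.21 D, inside the inclusion limit.
- With a plano sphere the same step gives -2.43 D, and with +6.00 D it gives -2.81 D, both outside it.

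A difference of plane therefore reconciles the limits for some prescriptions and not others. Both lists separately require the prescription to fall within the study lenses' available parameters.

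**Step 5: effect on the comparison.** Section 4 describes a bilateral crossover, and section 2 makes lens fitting characteristics the primary variable. Visit 1b fits both lenses in both eyes before Visit 2 dispenses the first pair. A subject who fails an entry criterion is lost to both lenses, and the same limit applies to each lens.

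**The case for a change.** The strongest case for a change is that an eligibility line should be clear where it stands. The neighbouring lines name their correction and this one does not, and naming it would cost a few words. The visit order does not settle the matter either, because the 20/30 study-lens line sits in the same lists and cannot be tested when the Visit 1a checklist is completed. With 40 subjects at one site, a few inconsistent decisions could alter who is described as enrolled.

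Much of this stands. The line is incomplete, the habitual-lens reading is plausible but unproved, and different readings could admit slightly different subjects. Two things limit its weight.

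First, the count of affected subjects rests on an assumption. If 1% to 5% of readings fell between the limits, 40 x 0.01 = 0.4 to 40 x 0.05 = 2.0 subjects would be affected when a subject's four readings (two eyes, two lenses) always agree. Treated as independent, they give 40 x (1 - 0.99^4) = 1.6 to 40 x (1 - 0.95^4) = 7.4. The documents support neither the share nor independence, and independence is implausible for the same eyes refitted. The figures also apply only on the study-lens reading.

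Second, most of Visit 1a, part of Visit 1b and the appendices are redacted. The acuity procedure and the lens it refers to may be stated there, so the visible gap cannot be taken as a gap in the full plan.

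**Conclusion.** No change to the plan is called for. The exclusion line leaves a detail unstated, but each reading of it gives a determinate answer once both lists are applied. The worst outcome is a redundant 20/30 limit over a band of 0.079 logMAR, about four letters. The cylinder difference is one 0.25 D step; on a single scale it alters nobody's eligibility, and otherwise it turns on an unstated plane.

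Choosing one reading over another could slightly shift the population enrolled. It would change no stated statistical figure and would treat neither lens differently in a comparison where each subject wears both. A site team can sensibly fill this gap when it completes the eligibility checklist.

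The conclusion rests on three points: both lists bind together, as section 8.1 says; one reading is used consistently for all subjects; and the primary comparison is the within-subject comparison of lens fit. No view is taken on which acuity or cylinder limit is right.

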## 8.2 Study Materials

### 8.2.1 Contact lens

All subjects will be trial fitted and, if suitable, dispensed the Avaira Vitality™ toric and ACUVUE OASYS® for ASTIGMATISM toric lenses. The study toric lenses and solutions will be provided by the Sponsor. Details of the contact lenses are shown in Table 1.

Table1: Study lenses

	Avaira Vitality™ toric	ACUVUE OASYS® for ASTIGMATISM
Manufacturer	CooperVision Inc.	Johnson & Johnson Vision Care
Material	fanfilcon A	senofilcon A
WC %	55%	38%
Base Curve	8.5 mm	8.6 mm
Lens Diameter	14.5 mm	14.5 mm
Lens Power Sphere	+8.00 to – 10.00	+6.00 to -10.00
Lens Power Cylinder	-0.75, -1.25, - 1.75, -2.25	-0.75, -1.25, - 1.75, -2.25
Wearing schedule	Daily wear	Daily wear

### 8.2.2 Contact Lens care

OPTI-FREE® PureMoist® multipurpose disinfecting solution and lens cases (Alcon, Fort Worth, TX) will be provided to all subjects for care and maintenance of the contact lenses during the study.

### 8.2.3 Storage of Study Medications/Treatments

There are no unapproved investigational products used in this study requiring special storage accommodations.

### 8.2.4 Clinical Supply Inventory

There are no unapproved investigational products used in this study requiring special inventory requirements.

### 8.2.5 Disposal of Consumables

This study dispenses consumables (lenses) to participants for use during the study. Study lenses worn for 2-weeks of daily wear by participants will be collected at the last visit and destroyed.

### 8.2.6 Masking and Control of Study Materials

The study contact lenses will be **masked to BOTH, the subject and investigator**. Study lenses will be transferred, by an assistant, out of their packaging to unmarked new contact lens cases filled

with unpreserved sterile saline just prior to dispensing to maintain subject masking of the study lenses.

### 8.2.7 Ordering and Accountability of Study Materials

The study lenses and solutions will be provided by the sponsor. If additional lenses are required, the study sponsor will re-supply the investigator as requested.

## 8.3 Visit Schedule and Procedures

---

### 8.3.1 Visit 1: Baseline and fitting visit (screening and enrollment)

The following evaluations will be performed to assess eligibility according to the Inclusion and Exclusion Criteria at the baseline visit only:

- The subjects should attend the first visit wearing their habitual contact lenses and having worn them that day for at least 2 hours prior to the visit. If they are not wearing their lenses, please reschedule the visit.
- The subject will be required to read and sign an Informed Consent Form prior to enrolment. When the subject has signed the consent form, the subject will be considered to be enrolled on to the study.
- The person explaining the consent and Investigator should also sign the consent form. Provide the subject with a copy and keep the original in the subject's paper chart or scan into the subject's electronic medical record (EMR) file.
- The subject is assigned with a Subject ID number. Subjects must be enrolled sequentially.
- Full anterior segment ocular health will be established

#### Visit 1a: Baseline habitual lenses

The following baseline measurements and assessments will be recorded:

[REDACTED]

[REDACTED]

- Habitual lens wearing times:

[REDACTED]

- Average daily wearing time (hours/day)
- Average comfortable wearing time (hours/day)

[REDACTED]

[REDACTED]

[REDACTED]

[REDACTED]

[REDACTED]

[REDACTED]

[Redacted text block]

[Redacted text block]

- [Redacted]
- [Redacted]
- [Redacted]
- [Redacted]
- [Redacted]

[Redacted text block]

[Redacted text block]

• Lens Fit

- Lens centration (centered/slightly decentered/substantially decentered)
- Corneal coverage [Y/N]
- Post-blink movement (0-5 Likert scale)

[Redacted text block]

[Redacted text block]

[Redacted text block]

[Redacted text block]

[Redacted text block]

[Redacted text block]

[Redacted text block]

[Redacted text block]

[Redacted text block]

[REDACTED]  
[REDACTED]  
[REDACTED]  
[REDACTED]

- Complete the eligibility checklist.
- If at this point the subject is found to be ineligible, then complete an Exit form and exit the subject from the study.

Visit 1 b: Fitting visit

If eligible, complete the Enrolment Log and identify the test lens from Appendix 4. The subjects will undergo a trial fit in both eyes with both study lenses (e.g. Avaira Vitality™ toric and ACUVUE OASYS® for ASTIGMATISM, according to manufacturer’s fitting guides) [REDACTED]

[REDACTED] If the lenses are not suitable to be dispensed then the subject will be discontinued and an Exit form will be completed.

**8.3.2 Visit 2: Dispense pair 1**

- Data is only collected on the final pair of study lenses dispensed after the power has been assessed and if needed corrected.
- Record the parameters of the lenses, lens type and power, on the Dispensing CRF (Appendix 6).

[REDACTED]  
[REDACTED]  
[REDACTED]  
[REDACTED]  
[REDACTED]  
[REDACTED]  
[REDACTED]  
[REDACTED]

- Lens centration (centered/slightly decentered/substantially decentered)
- Corneal coverage [Y/N]
- Post-blink movement (0-5 Likert scale)

[REDACTED]  
[REDACTED]  
[REDACTED]

[REDACTED]

- Lost or damaged study lenses may be replaced. Note which lens was replaced, date of replacement and reason for replacement on the Lens Replacement Log, (Appendix 6).

[REDACTED]

- Participants, who appear unable or unwilling to follow instructions to a degree that, in the Investigator's opinion, jeopardises the participant's wellbeing or the validity of the study, will be discontinued. The reason for discontinuation will be documented.
- The subject will be discharged and asked to return for a follow-up visit (V2) after 1-month.

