**8.3.3 Visit 3: 2-week follow-up pair 1 / dispenses pair 2**

The 2-week follow-up visit will be scheduled two weeks (**14 + 2 days**) from the initial lens dispensing date. The subject should wear the lenses for a minimum of 2 hours prior to the appointment. If the subject attends without lenses or with less than 2 hours of lens wear on that day and they are not having any problems with their lenses, the visit should be rescheduled, if possible within the visit window.

Visit 3a: Lens evaluation pair 1

- The following clinical test variables will be recorded on the Follow-Up Visit CRF:
  - Wearing times:

[REDACTED]

- Average daily wearing time (hours/day)
- Average comfortable wearing time (hours/day)

[REDACTED]

[REDACTED]

[REDACTED]

[REDACTED]

[REDACTED]

[REDACTED]

[REDACTED]

[REDACTED]

[REDACTED]

[REDACTED]

[REDACTED]

[REDACTED]

[REDACTED]

[REDACTED]

[REDACTED]

[REDACTED]

[REDACTED]

[REDACTED]

[REDACTED]

[REDACTED]

[REDACTED]

- Lens Fit
  - Lens centration (centered/slightly decentered/substantially decentered)
  - Corneal coverage [Y/N]
  - Post-blink movement (0-5 Likert scale)

[REDACTED]

[REDACTED]

[REDACTED]

[REDACTED]

[REDACTED]

[REDACTED]

[REDACTED]

[REDACTED]

Visit 3b: Dispense pair 2

The study subjects will undergo a trial fit in each eye with the second pair of study lenses.

- The performance of the second pair of study lenses should be assessed after 10-15 minutes settling time and the same variables as those collected on *visit 2* will be assessed.

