### 8.3.4 Visit 4: 2-week follow-up pair 2 / Exit

#### Visit 4a: Lens evaluation pair 2

The 2-week follow-up visit for pair 2 will be scheduled two weeks (**14 + 2 days**) from the initial lens dispensing date for pair 2. The subject should wear the lenses for a minimum of 2 hours prior to the appointment. If the subject attends without lenses or with less than 2 hours of lens wear on that day and they are not having any problems with their lenses, the visit should be rescheduled, if possible within the visit window. The same variables as those collected on section **8.3.3** will be assessed at this visit.

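### The return instruction at the end of section 8.3.2 (V2 after one month) contradicts the pair 1 follow-up in section 8.3.3 (Visit 3 at 14 + 2 days) in both interval and visit number

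*Combined protocol and SAP*

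**What the plan says.** Section 8.3.2 is headed as Visit 2, the dispensing of pair 1. It closes with the discharge instruction: "The subject will be discharged and asked to return for a follow-up visit (V2) after 1-month".

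Section 8.3.3, headed as Visit 3, covers the same return appointment: "The 2-week follow-up visit will be scheduled two weeks", with a window of 14 + 2 days counted from the initial dispensing. Section 8.3.4 repeats the pattern for the second period: "The 2-week follow-up visit for pair 2 will be scheduled two weeks", again with 14 + 2 days.

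The rest of the visible protocol agrees with two weeks:
- Section 1 speaks of two weeks of daily wear.
- Section 2 states the aim as refitting with the two lenses, ending "for Astigmatism lenses over 2-weeks of wear".
- Section 4 calls the trial a "2 week cross-over study comparing the fitting characteristics of senofilcon A toric lenses".
- Section 7 offers two-weekly monitoring as a way to limit adverse events.
- Section 8.2.5 says: "Study lenses worn for 2-weeks of daily wear by participants will be collected at the last visit and destroyed".

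Under the Visit 4b heading in section 8.3.4, the exit paragraph identifies study completion with Visit 3.

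**The concern.** The bullet stands where staff book the subject's next appointment, so it is an operative instruction. It conflicts with section 8.3.3 twice, on when the subject returns and on which visit that is. Both statements are unredacted, so no hidden text could make both true.

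A crossover compares two periods that are meant to be alike except for the lens. If the bullet were followed:
- Period 1 would run about a month and period 2 about two weeks.
- Pair 1 would stay in use beyond the two weeks that section 8.2.5 assumes.
- Lens fit, the primary variable, would be recorded at Visit 3a after the wrong exposure. So would wearing time, a secondary variable. In the visible text, wearing time with the study lenses is collected only at the follow-up visits.
- The two-weekly check in section 7 would not take place in period 1.

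**Working it through.** The plan gives no figure to reproduce here, so the check is date arithmetic on the stated intervals.

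**Inputs**
- Return interval in 8.3.2: one month, taken as 28 to 31 days.
- Pair 1 window in 8.3.3: 14 + 2 days, read as day 14 to day 16.
- Pair 2 window in 8.3.4: the same, day 14 to day 16.
- Minimum wear in the inclusion criteria of 8.1: "Is willing to comply with the wear schedule (at least 5 days per week".

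**Visit number.** The subject is leaving Visit 2 and is told to return for V2. Section 8.3.3 numbers the return Visit 3, so the label is one too low.

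**Distance outside the window.** Overshoot = one month − last day of window.
- Shortest: 28 − 16 = 12 days.
- Longest: 31 − 16 = 15 days.

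**Period 1 relative to period 2.** Ratio = one month ÷ length of period 2.
- Smallest: 28 ÷ 16 = 1.75.
- Largest: 31 ÷ 14 = 2.21.

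**First dispensing to exit.**
- As 8.3.3 and 8.3.4 intend: 2 × 14 = 28 to 2 × 16 = 32 days.
- With the bullet followed for pair 1: 28 + 14 = 42 to 31 + 16 = 47 days.

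**Wear days at the minimum schedule.**
- Period 1: 28 × 5/7 = 20.0 to 31 × 5/7 = 22.1.
- Period 2: 14 × 5/7 = 10.0 to 16 × 5/7 = 11.4.
- This restates the calendar ratio and is not separate evidence.

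**Effect on the lens comparison at follow-up.** Call the lenses A and B, and write m for a mean response after one month and w for one after two weeks. Leave aside any other period effect and any carryover.
- Sequence AB estimates A(m) − B(w).
- Sequence BA estimates A(w) − B(m).
- With equal weight on the two sequences, the average is ½{[A(m) − B(m)] + [A(w) − B(w)]}.

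If the lens difference does not depend on wear time, the unequal duration acts only as a period effect and cancels. If it does, the result mixes a one-month and a two-week difference, which is not the two-week comparison that the protocol describes.

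**Data not touched.** Fit at Visit 2 and at Visit 3b is assessed at dispensing, so it does not depend on how long pair 1 was worn under either reading.

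**The case against.** The strongest reply is that this is an obvious slip. Two weeks is stated in the introduction, objective, design, risk section, disposal section and both follow-up sections. One bullet disagrees, and it is visibly defective because it sends the subject back to the visit just attended. No one-month design appears anywhere in the visible text. There is one site, section 8.3.3 states the correct window, and no sample size, alpha or power figure depends on the bullet. All of this stands. It shows which reading is meant and limits the expected harm. It does not make the instruction correct, and no visible rule says which section prevails.

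The window might also have been printed as 14 ± 2 and misread in extraction. It would then be day 12 to 16 and the largest ratio would be 31 ÷ 12 = 2.6. It would still close on day 16, so the overshoot of 12 to 15 days would not change.

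Two stronger readings are tempting, and the documents support neither:
- A reader might infer that section 8.1 is also wrong, or that it backs the one-month bullet, because it describes "scheduled study visits over a period of approximately two months". That span includes the interval from Visit 1 to Visit 2, which the visible text does not give. Sections 8.3.1 and 8.3.2 contain redacted blocks where it could be stated. Section 8.1 therefore shows no error and does not decide between the two schedules.
- A reader might infer that all pair 1 follow-up data would be off schedule. That requires every subject to be booked by the bullet and nobody to apply the window in 8.3.3. It is a worst case, and nothing in the documents indicates how likely it is.

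**Conclusion.** Wrong as written. The last bullet of 8.3.2 conflicts with 8.3.3 in interval and in visit number, and the rest of the visible protocol supports 8.3.3. If followed, it would put the pair 1 follow-up 12 to 15 days beyond its window and make period 1 about 1.75 to 2.2 times as long as period 2. These sizes assume a month of 28 to 31 days, and the ratio also assumes a window of day 14 to 16.

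The harm is conditional on the site acting on the bullet. Even then, dispensing-visit fit data are intact, and the visible text does not say which time point is primary. A reader might infer a bias in favour of one lens. With balanced sequences, and a lens difference that does not change with wear time, the unequal duration is a period effect and not a lens bias. Balance is an assumption, since the visible text says only that the study is randomized.

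The Visit 3 label in the exit paragraph is a clerical slip with no effect on scheduling, because 8.3.4 itself defines Visit 4. Both labels are one too low, which suggests leftover text from a schedule with one fewer visit, but that origin is inference.

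**What to change.** In 8.3.2, replace the last bullet with an instruction to return for Visit 3 after two weeks (14 + 2 days) from dispensing. As a clerical matter, change the visit at which study completion occurs, in the Visit 4b exit paragraph, from Visit 3 to Visit 4.

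The cost is a few words in two places, with no added visits, procedures or subjects. The change is best made before enrolment. If any subject was dispensed pair 1 under the existing text, list the actual days from dispensing to Visit 3 so that follow-ups outside the window can be identified.
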